APPENDIX A: ECOG Performance Status Scale

| Grade | Description |
|-------|---|
| 0 | Normal activity. Fully active, able to carry on all pre-disease performance without restriction. |
| 1 | Symptoms, but ambulatory. Restricted in physically strenuous activity, but ambulatory and able to carry out work of a light or sedentary nature (e.g., light housework, office work). |
| 2 | In bed <50% of the time. Ambulatory and capable of all self-care, but unable to carry out any work activities. Up and about more than 50% of waking hours. |
| 3 | In bed >50% of the time. Capable of only limited self-care, confined to bed or chair more than 50% of waking hours. |
| 4 | 100% bedridden. Completely disabled. Cannot carry on any self-care. Totally confined to bed or chair. |
| 5 | Dead. |

APPENDIX B: Definitions for Adverse Event Reporting

A. Adverse Events (AEs)

As defined in 21 CFR 312.32:

Definition: any untoward medical occurrence associated with the use of a drug in humans, whether or not considered drug-related.

Grading: the descriptions and grading scales found in the revised NCI Common Terminology Criteria for Adverse Events (CTCAE) version 5.0 will be utilized for all toxicity reporting. A copy of the CTCAE version 5.0 can be downloaded from the CTEP website.

Attribution (relatedness), Expectedness, and Seriousness: the definitions for the terms listed that should be used are those provided by the Department of Health and Human Services' Office for Human Research Protections (OHRP). A copy of this guidance can be found on OHRP's website:

<http://www.hhs.gov/ohrp/policy/advevntguid.html>

B. Suspected Adverse Reaction (SAR)

As defined in 21 CFR 312.32:

Definition: any adverse event for which there is a reasonable possibility that the drug caused the adverse event. “Reasonable possibility” means there is evidence to suggest a causal relationship between the drug and the adverse event. “Suspected adverse reaction” implies a lesser degree of certainty about causality than adverse reaction, which means any adverse event caused by a drug.

C. Life-Threatening Adverse Event / Life Threatening Suspected Adverse Reaction

As defined in 21 CFR 312.32:

Definition: any adverse drug event or suspected adverse reaction is considered “life-threatening” if, in the view of the investigator, its occurrence places the patient at immediate risk of death. It does not include an adverse event or suspected adverse reaction that, had it occurred in a more severe form, might have caused death.

D. Serious Adverse Event (SAE) or Serious Suspected Adverse Reaction

As defined in 21 CFR 312.32:

Definition: an adverse event or suspected adverse reaction is considered “serious” if, in the view of the investigator, it results in any of the following outcomes:

- Death

- A life-threatening adverse event
- Inpatient hospitalization or prolongation of existing hospitalization
- A persistent or significant incapacity or substantial disruption of the ability to conduct normal life functions
- A congenital anomaly/birth defect
- Any other important medical event that does not fit the criteria above but, based upon appropriate medical judgment, may jeopardize the subject and may require medical or surgical intervention to prevent one of the outcomes listed above

E. Protocol Exceptions

Definition: A planned change in the conduct of the research for one participant.

F. Deviation

Definition: Any alteration or modification to the IRB-approved research without prospective IRB approval. The term “research” encompasses all IRB-approved materials and documents including the detailed protocol, IRB application, consent form, recruitment materials, questionnaires/data collection forms, and any other information relating to the research study.

A minor or administrative deviation is one that does not have the potential to negatively impact the rights, safety, or welfare of participants or others or the scientific validity of the study.

A major deviation is one that does have the potential to negatively impact the rights, safety, or welfare of participants or others or the scientific validity of the study.

APPENDIX C: Reporting Timelines

| Expedited Reporting Timelines | | |
|--|---|---|
| Event | HRPO | QASMC |
| Serious AND unexpected suspected adverse reaction | | |
| Unexpected fatal or life-threatening suspected adverse reaction | | |
| Unanticipated problem involving risk to participants or others | Report within 10 working days. If the event results in the death of a participant enrolled at WU/BJH/SLCH, report within 1 working day. | Report via email after IRB acknowledgment |
| Major deviation | Report within 10 working days. If the event results in the death of a participant enrolled at WU/BJH/SLCH, report within 1 working day. | |
| A series of minor deviations that are being reported as a continuing noncompliance | Report within 10 working days. | |
| Protocol exception | Approval must be obtained prior to implementing the change | |
| Clinically important increase in the rate of a serious suspected adverse reaction of that listed in the protocol or IB | | |
| Complaints | If the complaint reveals an unanticipated problem involving risks to participants or others OR noncompliance, report within 10 working days. If the event results in the death of a participant enrolled at WU/BJH/SLCH, report within 1 working day. Otherwise, report at the time of continuing review. | |
| Breach of confidentiality | Within 10 working days. | |
| Incarceration | If withdrawing the participant poses a safety issue, report within 10 working days. If withdrawing the participant does not represent a safety issue and the patient will be withdrawn, report at continuing review. | |

| Routine Reporting Timelines | | |
|--|---|--|
| Event | HRPO | QASMC |
| Adverse event or SAE that does not require expedited reporting | If they do not meet the definition of an unanticipated problem involving risks to participants or others, report summary information at the time of continuing review | Adverse events will be reported in the toxicity table in the DSM report which is typically due |

| Routine Reporting Timelines | | |
|-----------------------------|---|-----------------|
| Event | HRPO | QASMC |
| | | every 6 months. |
| Minor deviation | Report summary information at the time of continuing review. | |
| Complaints | If the complaint reveals an unanticipated problem involving risks to participants or others OR noncompliance, report within 10 working days. If the event results in the death of a participant enrolled at WU/BJH/SLCH, report within 1 working day. Otherwise, report at the time of continuing review. | |
| Incarceration | If withdrawing the participant poses a safety issue, report within 10 working days. If withdrawing the participant does not represent a safety issue and the patient will be withdrawn, report at continuing review. | |

APPENDIX D: PRO-CTCAE Inventories

All patients will complete the following PRO-CTCAE inventories:

- Rash
- Numbness/tingling
- Dizziness
- Concentration
- Memory
- General pain
- Fatigue
- Insomnia
- Anxious
- Discouraged
- Sad

Patients with GI cancers (including esophagus, lower GI, and retroperitoneal sarcoma) will complete the following additional PRO-CTCAE inventories:

- Decreased appetite
- Nausea
- Vomiting
- Heartburn
- Gas
- Bloating
- Hiccups
- Constipation
- Diarrhea
- Abdominal pain
- Fecal incontinence

Patients with thoracic cancers (including esophagus, lung, and chest wall) will complete the following additional PRO-CTCAE inventories:

- Decreased appetite
- Nausea
- Vomiting
- Heartburn
- Gas
- Bloating
- Hiccups
- Shortness of breath
- Wheezing
- Voice changes
- Hoarseness

Patients with pelvic cancers (including prostate, gynecologic, sarcomas, rectum, anus) will complete the following additional PRO-CTCAE inventories:

- Vaginal discharge
- Vaginal dryness
- Painful urination
- Urinary urgency
- Urinary frequency
- Change in urine color
- Urinary incontinence
- Erection
- Ejaculation
- Libido
- Delayed orgasm
- Unable to have orgasm
- Pain with intercourse

Patients with head and neck cancers will complete the following additional PRO-CTCAE inventories:

- Dry mouth
- Swallowing
- Mouth sores
- Cheilitis
- Voice changes
- Hoarseness

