1.7 Risk/Benefit Assessment

1.7.1 Known Potential Risks

High-dose radiation has been known to cause toxicity to normal tissue. This is manifested variably depending on the area of the body treated. While the potential toxicities can be serious and include death, these toxicities are rare when high-quality, high-dose radiation is delivered within established normal tissue dose constraints using appropriate immobilization, image guidance, and institutional experience. We have successfully tested many Lattice SBRT plans prescribed to 66.7 Gy in 5 fractions using institutional quality assurance protocols similar to conventional SBRT. Therefore, we expect the toxicity risks associated with Lattice SBRT plans to be similar to conventional SBRT if the required established dose constraints are met.

Blood collection prior to and after radiotherapy poses a small risk of pain and bleeding.

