2.0 OBJECTIVES AND ENDPOINTS

| Objectives | Endpoints | Justification for Endpoints |
|--|---|---|
| Primary | | |
| To evaluate the safety of palliative Lattice SBRT in patients with non-hematologic malignancies with large lesions in need of palliative radiotherapy (≥ 4.5 cm) | Rate treatment-related, non-hematologic CTCAE v5.0 Grade ≥ 3 toxicity | SBRT to large tumors is traditionally associated with high dose to OARs, with sequelae of radiation-induced toxicities. As these patients have no effective treatment options, evaluation of the safety of this method of dose-escalation with SBRT is warranted. CTCAE v5.0 is a widely accepted standardized measure of treatment-related toxicity. |
| Exploratory | | |
| To assess pain response to Lattice SBRT | For patients that have pain, their pain level will be assessed with the pain Numeric Rating Scale (NRS) | The NRS is an 11-point scale for patient self-reporting of pain. This is selected because it is a reliable and clinically meaningful measure of pain that is extensively used in research and clinical practice. |
| To assess patient-reported toxicity outcomes | For patients that do not have pain, patient-reported symptom response will be assessed with PRO-CTCAE | PRO-CTCAE is a standardized inventory to collected patient reported symptomatic adverse events in clinical trials. |
| To assess patient reported quality of life outcomes | Patient reported quality of life and functional outcomes will be measured before treatment, after treatment, and at each follow up with the PROMIS Global, Physical Function, Pain Interference, Anxiety, and Depression system | This patient reported outcome inventory was selected because it is a reliable and clinically meaningful measure of patient reported toxicities and functional outcomes. |
| To evaluate blood for immune- and tumor damage-associated response with Lattice SBRT | Whole blood will be collected at baseline and after Lattice SBRT for exploratory studies of immune and tumor damage associated-response | The response of immune-related markers will be assessed before and after Lattice SBRT to better understand the immunogenic effects of treatment on tumor. |

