5.4 Patient-Reported Quality of Life Outcome and Toxicity Measures

Symptom response and patient-reported quality of life will be measured using the pain numeric rating scale, PRO-CTCAE (abridged as indicated in Appendix D), PROMIS Global, Physical Function, Pain Interference, Anxiety, and Depression questionnaire at the following time points:

1. Within 2 weeks prior to the start of radiotherapy
2. Within 2 weeks after completion of radiotherapy
3. At 30 days after radiotherapy
4. At 90 days after radiotherapy

The patient reported outcomes measures will be conducted using a computer-assisted interview program and may be done in person before/after a routine office visit or over the phone at the preference of the study participant. Patient reported outcomes may also be collected online.

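### Appendix D assigns the added PRO-CTCAE lists by type of cancer, not by the region irradiated, so some region-specific patient-reported symptoms go unasked

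*Combined protocol and SAP*

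**What the plan says.** Appendix D opens with a core list: "All patients will complete the following PRO-CTCAE inventories". It then adds four lists, each tied to a diagnosis:

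- GI: "Patients with GI cancers (including esophagus, lower GI, and retroperitoneal sarcoma) will complete the following additional PRO-CTCAE inventories"
- Thoracic: "Patients with thoracic cancers (including esophagus, lung, and chest wall) will complete the following additional PRO-CTCAE inventories"
- Pelvic: "Patients with pelvic cancers (including prostate, gynecologic, sarcomas, rectum, anus) will complete the following additional PRO-CTCAE inventories"
- Head and neck: "Patients with head and neck cancers will complete the following additional PRO-CTCAE inventories"

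Section 5.4 gives no other selection rule. It names the instrument as "PRO-CTCAE (abridged as indicated in Appendix D") and sets four time points: before radiotherapy, within 2 weeks after it, and at 30 and 90 days.

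The items serve an exploratory objective in Section 2.0: "To assess patient-reported toxicity outcomes". On radiation toxicity, Section 1.7.1 says: "This is manifested variably depending on the area of the body treated".

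**The concern.** The symptoms a radiation field can cause depend on what lies in the field. In this trial the field need not be where the cancer began. Section 3.1 sets no limit by primary site and asks only for a lesion of at least 4.5 cm planned for palliative radiotherapy. Section 5.3.2.1 foresees spine lesions as targets, and Section 5.1 allows up to 4 other tumor sites to be treated. A rule based on diagnosis can therefore issue a list for one region while another is irradiated, or issue no regional list at all.

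At stake is the patient-reported description of toxicity for a new technique in a trial whose purpose is safety. An item that was never asked cannot be recovered later, and a missing baseline cannot be rebuilt.

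**Working it through.** The documents state no figure on this point, so the check is to count the items in Appendix D and apply the rule as written.

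**Counts.** Core 11, GI 11, thoracic 11, pelvic 13, head and neck 6.

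**Overlap.** GI and thoracic share 7 items (appetite, nausea, vomiting, heartburn, gas, bloating, hiccups). Thoracic and head and neck share 2 (voice changes, hoarseness). The pelvic list shares none with the others.

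**Sex-specific items.** The pelvic list has 2 vaginal items and 2 on erection and ejaculation, so at most 13 − 2 = 11 apply to any one patient.

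**Bowel items.** Diarrhea, constipation, abdominal pain and fecal incontinence appear only in the GI list.

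| Primary and Lattice target | Lists issued | Regional items not asked |
|---|---|---|
| Lung, treated in the lung | Core + thoracic | None from the thoracic list |
| Lung, treated in the pelvis | Core + thoracic | All pelvic items (at most 11 apply) and the 4 bowel items |
| Prostate, treated in the chest | Core + pelvic | All 11 thoracic items, including shortness of breath and wheezing |
| Rectum, treated in the lung | Core + pelvic, plus GI if counted as lower GI | Shortness of breath, wheezing, voice changes and hoarseness (11 − 7 = 4 even if GI is given) |
| Melanoma or breast, any target | Core only | The whole list for the region treated: 6, 11 or 13 items |
| Prostate or gynecologic, treated in the pelvis | Core + pelvic | The 4 bowel items |

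The rows show three separate gaps:

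1. **Target outside the region of the primary.** The list follows the diagnosis and misses the field. Where the two coincide, as in the first row, this gap does not arise.
2. **Primary on no list.** The patient gets no regional items wherever the field lies. This is an absence of items rather than items for another organ.
3. **Matched pelvic field without a GI diagnosis.** No bowel item is asked, although Section 5.3.2.3 sets dose limits for rectum, colon and jejunum/ileum. This gap needs no mismatch.

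**Share affected.** Gaps 1 and 2 depend on how many patients are treated away from their primary or have an unlisted primary. The documents give no figure, so the range is 0% to 100%, whether 10 patients are enrolled (Synopsis) or 20 (Section 11.1).

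**Who completes the form.** Section 2.0 assigns PRO-CTCAE to patients without pain, Section 5.2 lists it at baseline only where applicable, and Appendix D gives it to everyone. These three statements do not agree.

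**The case against.** The strongest reply is that much toxicity information is collected whatever the diagnosis. Every patient answers the core items, which include rash, numbness, general pain and fatigue. Section 5.4 adds the pain NRS and PROMIS. The Schedule of Activities has clinician AE review at fraction 5, end of treatment, 30 days and 90 days. Under Section 7.0 that review records gastrointestinal, urinary, respiratory, nervous system and skin events above grade 1. All of this stands. A reader might infer that in-field toxicity is not asked about at all, and the documents do not support that. The clinician route does not close the gap entirely, because Section 7.0 leaves grade 1 events, and any event outside eight categories, off the toxicity form.

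Second, some headings are anatomical, so staff might apply them by lesion location. They might, but the text does not say so. A related inference would be that every sarcoma patient gets the urinary and sexual items. That does not hold: the word stands inside a list of pelvic cancers, while chest wall appears under thoracic and retroperitoneal sarcoma under GI.

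Third, Section 2.0 describes the PRO-CTCAE endpoint as symptom response, which could favor following the disease. But the symptoms expected to respond are those of the treated lesion, and they too follow its location.

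Fourth, the consequence is limited. Section 11.2 does not name PRO-CTCAE among the exploratory endpoints, and Section 11.3 plans a before-and-after test only for QoL scores. This also stands. A reader might infer that the results would look falsely reassuring, but no planned PRO-CTCAE analysis exists on which to base that claim.

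**Conclusion.** The point holds. As written, the rule omits region-specific patient-reported symptoms for patients whose Lattice target lies outside the region of their primary, for patients whose primary is on no list, and, for bowel symptoms, for prostate or gynecologic patients treated in the pelvis. The number of items lost runs from 4 (bowel items in a matched pelvic field) to the full list for the treated region.

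The effect is confined to an exploratory objective. The primary endpoint, sample size and stopping boundary are untouched. A reader might suppose that most patients are affected or that a mismatched patient has no relevant item. Neither follows: the share is unknown, and some lists overlap by up to 7 of 11 items. The conclusion rests on Appendix D being applied as written and on PRO-CTCAE being given to all patients, which Section 2.0 puts in doubt. The change is cheap and worth making, because unasked items cannot be recovered.

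**What to change.** Reword Appendix D as follows:

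- Assign the added lists by the region or regions in the Lattice SBRT field: abdomen for the GI list, thorax, pelvis, and head and neck. Give every list that applies, and use the same list or lists at all four time points. Tying the rule to the Lattice field avoids mixing in symptoms from other sites treated with other techniques.
- Add the existing diarrhea, constipation, abdominal pain and fecal incontinence items for pelvic fields.
- State that fields outside these regions, such as an extremity, get the core list only.
- If any diagnosis label is kept, write pelvic sarcomas.
- Reconcile Sections 2.0 and 5.2 with Appendix D on who completes PRO-CTCAE.

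**Cost.** No new instrument is needed. A matched prostate or gynecologic patient with a pelvic field answers 4 more items. A patient who now gets no added list answers 6 more (head and neck), 11 more (thorax or abdomen) or 13 + 4 = 17 more (pelvis, of which at most 17 − 2 = 15 apply to one patient). Some mismatched patients would drop items for a region that is not treated. The Lattice target region must be known before the baseline form is issued; because the lesion is itself an eligibility criterion, it normally will be.
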